Safety will be determined by the occurrence of any adverse events (AE) or serious adverse events (SAE). In accordance with the GCP decision tree for adverse event reporting all events will be reported to the sponsor and recorded to determine the safety of the intervention.

Utility will include eligibility (n = eligible/screened), recruitment (recruited/eligible), and adherence (number of patients completing the HIIT programme). The number of patients screened, recruited and commencing the HIIT programmes will be monitored at each hospital site. A register (if required, i.e. more than one patient attending), will be taken at each exercise class to record patient adherence and the completeness of each session will be recorded (i.e. how many minutes the patient completed). It is estimated that all patients should complete 18 sessions in total within 6 weeks. However, where any sessions are missed, the intervention period can be extended to 8 weeks to allow these sessions to be added on. Those not completing 18 sessions over the extended 8-week period will be deemed to have satisfactorily completed the intervention as long as they have completed >80% of the intervention (i.e. ≥ 15 out of 18 sessions). All patients completing the allotted 6-8 weeks for the intervention (regardless of whether they have completed \geq or < 15 sessions) will still be followed up. Those choosing to discontinue the intervention before completing the full intervention timeframe will be withdrawn.

Tolerability will be assessed by identifying if patients are able to reach and maintain the prescribed training range required to perform HIIT, for each full interval. Heart rate (HR) data will be collected throughout each HIIT session and saved on an encrypted USB stick this will then be compared to the 85-100%HRMax training range that has been prescribed – to determine if patients are able to achieve it. This range will be in line with an ongoing HIIT trial in CAD at 85-90% peak power output (PPO), aiming to achieve >85%HRMax, derived from CPET (15). If patients are not able to achieve 85-100%, this will determine the suitability of this HIIT protocol in this population. Reasons for stopping the HIIT exercise sessions (e.g. leg pain), will be recorded.

Secondary endpoints

Acceptability

Acceptability will be assessed by patient feedback using semi-structured interviews.

conducted using a sample of patients in three groups:

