This study will use a pragmatic and flexible HIIT protocol with a higher intensity than that previously used in the IC population (12). The protocol will consist of 3 sessions per week for 6 weeks, with a work to rest ratio of 1:1 (one-minute interval of HIIT interspaced by one-minute interval of low-intensity exercise), completing 10 sets of HIIT with an overall exercise session time of 20 minutes. The intensity will be set at 85-90% PPO (from CPET) during high-intensity, (aiming to achieve 85-100% HRMax), and at 20-25%PPO during low-intensity bouts. The variation from high to low intensity will be achieved by altering the cycle cadence (rpm). This work to rest ratio has been selected as although HIIT is often prescribed in similar clinical populations using 4-minute intervals at 85-95%HRMax (33), a large RCT recently concluded that HIIT at this intensity is hardly feasible, at least not for a full 4-minutes (15). Our personal experience with cardiac patients has demonstrated that patients may exceed their peak heart rate (from CPET) during HIIT sessions. This is also likely to be the case for those with IC, especially those who are unable to achieve a maximal effort CPET. We will adopt a pragmatic approach to this by allowing it to occur but monitoring on a case-by-case basis and will reduce intensity when deemed appropriate. We will also record these occurrences to allow appropriate reporting.

The HIIT sessions will be preceded and followed by a 10-minute warm up and cool down as is standard practice in exercise rehabilitation for older adults with chronic disease. In addition, patients will be monitored for up to 10 minutes following the cool-down to ensure heart rate is returning to near resting values and/or any symptoms have subsided.

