Data obtained from all participants will be included in the data analysis and no data will be excluded on the basis of intervention and follow-up adherence. Therefore, all collected data at each time point will be analysed.

Baseline characteristics will be summarised descriptively using mean (\pm SD) for normally

distributed data and using median and range for non-normally distributed data. Categorical variables will be presented as frequency and percentages.

Rates of uptake, completion, dropout, adverse or serious adverse events and missing outcome data will be summarised and participation in the intervention will be described as the mean number of sessions attended and the mean time to completion (in weeks) to allow for comparison between actual and theoretical total intervention time.

In addition, tolerability will be assessed by comparing the mean heart rate achieved during each HIIT session to the 85-100% maximum heart rate range calculated from CPET.

Secondary endpoints such as changes in MWD, PFWD, VO_{2Peak} , VAT, ABPI and QoL at each time-point will be assessed using a repeated-measures general linear model.

All quantitative analyses will be conducted using the SPSS statistics software at the conventional two-sided 5% significance level with results presented as mean difference with 95% confidence intervals, associated *p* values and effect sizes where appropriate. Sub-group analysis will also be conducted comparing those who are able to give maximal effort during baseline CPET (and therefore able to perform maximal HIIT) and those who are not (therefore performing submaximal HIIT). Maximal effort will be based on previously published criteria (19, 38). Further sub-group analysis will also be performed comparing those who satisfactorily completed the intervention (i.e. completed $\geq 15/18$ sessions) and those who did not, presuming they do not withdraw from the intervention.

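### Read literally, the tolerability definition (in the heart-rate range for every full one-minute interval) scores heart-rate lag, and the planned session mean does not measure it

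*Combined protocol and SAP*

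**What the plan says.** Tolerability is one of three primary components, with utility and safety. All references are to the combined protocol and SAP.

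- **Measurement of primary and secondary endpoints, tolerability paragraph.** The test is whether patients are "able to reach and maintain the prescribed training range required to perform HIIT, for each full interval". Heart rate is recorded throughout each session and "compared to the 85-100%HRMax training range that has been prescribed", so the range is a heart-rate range. The stated purpose is "to determine if patients are able to achieve it", and a consequence follows: "If patients are not able to achieve 85-100%, this will determine the suitability of this HIIT protocol in this population".
- **Intervention, HIIT programme.** The structure is "one-minute interval of HIIT interspaced by one-minute interval of low-intensity exercise", "completing 10 sets of HIIT with an overall exercise session time of 20 minutes". Workload is the prescription and heart rate the aim: "The intensity will be set at 85-90% PPO (from CPET) during high-intensity, (aiming to achieve 85-100% HRMax), and at 20-25%PPO during low-intensity bouts". The same section expects that some patients will exceed their CPET peak heart rate, and allows it.
- **Descriptive statistics and statistical analysis.** Tolerability is assessed by "comparing the mean heart rate achieved during each HIIT session to the 85-100% maximum heart rate range". The section does not say whether the low-intensity minutes, warm-up or cool-down enter the mean.

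No section gives a pass mark for an interval, session, patient or cohort, or says how values above 100% are scored.

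**The concern.** Heart rate moves continuously and follows workload with a delay. To be in range for a whole work minute it must be at 85% HRMax or more when that minute begins. For interval 1 that is the end of the warm-up. For intervals 2 to 10 it is the end of a minute at 20-25% PPO, whose purpose is to let heart rate fall. A literal scorer would therefore mark down patients who did all the prescribed work.

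The protocol makes the suitability of the programme depend on this outcome. Two analysts with the same traces could report opposite answers, one using whole intervals and the other using the level reached in each interval. Aligning the statistics section to the endpoint wording would not help, because it would carry the lag problem into the analysis.

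**Working it through.** **Plan's own figure.** 10 × (1 + 1) min = 20 min, as stated. There is no powered calculation to reproduce.

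**Model (assumed; the documents give no kinetics).** Heart rate in % HRMax approaches a target exponentially: H(t) = target + (H(0) − target) × exp(−t/τ). It is run in 1-second steps for ten cycles of 60 s work and 60 s recovery, with every bout completed.

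**What a full interval needs.** If work ends at level W and recovery tends to L, the next bout starts at L + (W − L) × exp(−60/τoff), which must be at least 85. With W = 100 for illustration:
- L = 60: exp(−60/τoff) ≥ 25/40 = 0.625, so τoff ≥ 60/0.470 = 128 s.
- L = 70: ≥ 15/30 = 0.5, so τoff ≥ 60/0.693 = 87 s.
- L = 75: ≥ 10/25 = 0.4, so τoff ≥ 60/0.916 = 65 s.

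So the answer for later intervals depends on how high heart rate stays in recovery. Interval 1 depends only on where the warm-up ends.

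**One central case.** Assume heart rate is 60% HRMax at zero load and linear in power, with τon = 30 s and τoff = 45 s.
- Work target: 60 + 40 × 0.875 = 95. Recovery target: 60 + 40 × 0.225 = 69. Start: 60 + 40 × 0.20 = 68.
- Bout 1 reaches 85 after 30 × ln(27/10) = 29.8 s, so about half the minute is in range. It ends at 95 − 27 × exp(−2) = 91.3.
- The next bout starts at 69 + 22.3 × exp(−60/45) = 74.9. By bout 10 about 66% of the minute is in range, ending at 92.3.
- The mean over the 20 minutes is 84.0.

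This session fails the whole-interval definition, achieves the range in every bout, and narrowly misses 85% on the session mean.

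**Grid of 36.** τon 20, 30, 45, 60 s; τoff 40, 60, 90 s; work target 95, 100, 105; 4 × 3 × 3 = 36. Recovery target and starting level are set equal. Only the 85% floor is scored for whole intervals; a 100% ceiling could only lower those counts.

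| Recovery and start (% HRMax) | All ten wholly in range | At least one wholly in range | Peak ≥85% in at least nine |
|---|---|---|---|
| 60 | 0/36 | 0/36 | 35/36 |
| 70 | 0/36 | 4/36 | 36/36 |
| 75 | 0/36 | 11/36 | 36/36 |

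At 60% recovery, time in range over the work minutes runs from 0 to 94%. The session mean including easy minutes is at or above 85% in 13 of 36, so it is below in 36 − 13 = 23. At least 35 − 13 = 22 scenarios reach 85% in nine or more intervals but miss it on the mean.

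**Wider grid of 1,080** (zero-load heart rate 50-75% HRMax, τon 15-60 s, τoff 30-90 s, 0 to 10 points added at the high workload):
- All ten intervals wholly in range: 0.
- At least one: 242 (22%). At least nine: 209 (19%).
- End-of-interval heart rate ≥85% in all ten: 1,036 (96%).
- Session mean ≥85%: 789 (73%).
- End-of-interval ≥85% in all ten but session mean below 85%: 247 (23%).

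**Check on the replacement score.** If a peak had to lie between 85% and 100%, only 29 of 36 scenarios at 60% recovery would score nine or ten intervals, against 35 of 36 with the floor alone. The ceiling would fail completed bouts that the intervention section expects and allows.

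**The case against.** The strict reading is not the only one. To reach a range implies a rise into it, so the sentence may mean rise, then hold to the end of the bout. The same paragraph later asks only whether the range is achieved, and intensity is prescribed by workload. This stands as a possible reading, but the text does not choose it, and a primary outcome should not depend on which reading the analyst takes.

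A reader might infer that one-minute bouts can never produce a wholly in-range interval. The documents do not support that. They give no kinetics, and in the model later intervals are wholly in range when recovery heart rate stays high. The zero for all ten also depends on the first bout starting below 85%: the starting level was 60-75% in the table and 60-80% in the wider grid.

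A reader might also infer that well-performed HIIT will fail the trial's primary criterion. That goes too far. No numeric criterion exists, tolerability is one of three components in a descriptive proof-of-concept study, and the planned statistic is the session mean, which most scenarios in the wider grid pass. But the session mean does not rescue the definition: it measures something else, and it puts some completed sessions below 85%.

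**Conclusion.** The concern holds in this form. Taken literally, the definition measures heart-rate lag, and a patient who completes every bout would not meet it for all ten intervals unless heart rate were already at 85% HRMax when the first bout began and stayed there through each recovery minute. It was met in 0 of 36 scenarios at each recovery level tried and in 0 of 1,080 in the wider grid. Judged on the level reached within each interval, nearly all the same sessions succeed.

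The lag argument needs only that heart rate is continuous. The counts rest on assumed first-order kinetics and recovery levels, and show sensitivity to the scoring rule; they do not forecast results in these patients. The mismatch between the endpoint section and the statistics section can be read from the text without any model.

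**What to change.** Use one per-interval score in both the tolerability paragraph and the statistics section, replacing the whole-interval wording and the session-mean comparison:

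- An interval counts as achieved if peak heart rate in the work minute is at or above 85% of CPET HRMax.
- Values above 100% count as achieved and are reported separately.
- Report the proportion of intervals achieved per session and per patient, with interval 1 shown separately.
- Keep time in range and session mean as descriptive only, and state which minutes enter the mean.

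The cost is a sentence in each section and a scoring rule applied to the trace already collected. The downside is that a peak-based score is less strict than continuous time in range, which is why time in range should still be shown. The exercise prescription does not change.

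### The planned tolerability analysis uses only exercise that was performed, so it does not implement the protocol's own per-interval definition and may overstate tolerability

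*Combined protocol and SAP*

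**What the plan says.** Tolerability is one of three components of the primary endpoint. The section on measuring the primary endpoint asks whether patients are "able to reach and maintain the prescribed training range required to perform HIIT, for each full interval". It gives the result a consequence: "If patients are not able to achieve 85-100%, this will determine the suitability of this HIIT protocol in this population". It ends by noting that "Reasons for stopping the HIIT exercise sessions (e.g. leg pain), will be recorded".

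The section on descriptive statistics and statistical analysis contains the only planned analysis: "tolerability will be assessed by comparing the mean heart rate achieved during each HIIT session to the 85-100% maximum heart rate range", with the maximum taken from CPET. It keeps all collected data from all participants whatever their adherence. It also plans summaries of completion, dropout and sessions attended, and rules out imputation.

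The HIIT programme section sets the prescription: "completing 10 sets of HIIT with an overall exercise session time of 20 minutes". The primary-endpoint section expects 18 sessions per patient.

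Stopping and leaving are dealt with under utility. There, "the completeness of each session will be recorded (i.e. how many minutes the patient completed" covers minutes done, adherence is defined as "adherence (number of patients completing the HIIT programme", and for early leavers, "Those choosing to discontinue the intervention before completing the full intervention timeframe will be withdrawn".

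**The concern.** The definition is about every full interval, whereas the analysis is about a session mean. An interval that was not performed has no heart rate, so it cannot pull that mean down or register as a failure. Minutes completed and stopping reasons are collected, but no planned tolerability analysis uses them.

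This matters because the protocol lets this outcome decide whether the HIIT regimen suits the population, and itself names leg pain as a reason a session might be stopped. A patient who reaches the target heart rate and then has to stop has not maintained the range for each full interval, yet can be scored as in range.

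The session-based completion rule would not necessarily expose this. Satisfactory completion means at least 15 of 18 sessions, and no minimum content is stated for a session to count.

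**Working it through.** **Inputs from the protocol.** 10 intervals per session (HIIT programme section); 18 sessions per patient (primary-endpoint section); 50 patients at Hull and 20 at Coventry (sample size section).

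The plan's only relevant total reproduces: 50 + 20 = 70. It states no tolerability rate, threshold or expected dropout, so there is no tolerability figure to reproduce. Prescribed exposure is 18 × 10 = 180 intervals per patient and 70 × 18 = 1,260 sessions overall.

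**Step 1: definition against analysis.** Take a session stopped after 4 of 10 intervals, with heart rate in range for those 4.

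- Under the definition, the range was held for 4/10 = 40% of prescribed intervals, so the patient did not manage each full interval.
- Under the planned analysis, the mean is taken over the performed part only. If that mean lies within 85-100%, the session is in range.

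The two sections therefore give opposite answers for the same session. An interval-level summary limited to recorded intervals would not help: it gives 4/4 = 100%.

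**Step 2: weight of early withdrawers.** The protocol does not say whether sessions are pooled across patients. The following is an illustration with assumed rates: patients who stay do 18 sessions with 90% in range, and withdrawers do 3 sessions with 50% in range. Let Nc be the number who stay and Nw the number who withdraw.

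- Pooled over performed sessions = (18 × Nc × 0.9 + 3 × Nw × 0.5) / (18 × Nc + 3 × Nw)
- Equal weight per patient = (Nc × 0.9 + Nw × 0.5) / 70
- Over all planned sessions, unperformed counted as failed = (18 × Nc × 0.9 + 3 × Nw × 0.5) / 1,260

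| Withdraw | Pooled, performed | Equal weight per patient | All planned sessions |
|---|---|---|---|
| 7 of 70 (10%) | 1,031.1/1,155 = 89.3% | 60.2/70 = 86.0% | 81.8% |
| 14 of 70 (20%) | 928.2/1,050 = 88.4% | 57.4/70 = 82.0% | 73.7% |
| 21 of 70 (30%) | 825.3/945 = 87.3% | 54.6/70 = 78.0% | 65.5% |

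At 20% withdrawal, the 14 withdrawers supply 14 × 3 = 42 of 1,050 session records (4.0%). As withdrawal triples from 10% to 30%, the pooled figure moves by only 2.0 points (89.3% to 87.3%).

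**Step 3: sensitivity at 20% withdrawal.** Let withdrawers' in-range rate run from 0 to 90% and their sessions from 1 to 6. The pooled figure runs from 83.1% to 90.0%, the per-patient figure from 72.0% to 90.0%, and the planned-session figure from 72.0% to 78.0%. If withdrawers were in range as often as everyone else (90%), pooled and per-patient figures agree, so the pooling effect is not inevitable.

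The planned-session column is an outer bound. It fails every session not attended, whatever the reason, which is further than the fix below goes.

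**The case against.** A reader might infer that unperformed intervals are excluded by rule and that intolerant patients vanish from the primary endpoint. The documents do not support that, for four reasons.

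- The exclusion would be read from silence. The per-interval definition can fairly be read as failing an interval that was not done, and the note on stopping reasons sits in the tolerability paragraph, so it may be meant to inform the assessment.
- The statistical section keeps all data from all participants. Heart rate up to the point of stopping or withdrawal is analysed, and low values there would show.
- Completion is itself part of the primary endpoint, under utility. Dropout and sessions attended are summarised, and discontinuers form one of the interview groups. High dropout would appear beside any favourable heart-rate result.
- Pooling is not stated. Per-patient summaries would remove the weighting problem.

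It can also be said that keeping intensity and completion separate is a legitimate descriptive choice, and that scoring withdrawal as not tolerated counts one event twice. Participants may also withdraw without giving a reason, so such a score could not always be applied. Finally, this is a single-arm proof-of-concept study with no tolerability threshold or stated test of it.

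These arguments rule out the stronger reading and keep withdrawal out of the main tolerability score. They do not remove the mismatch. Keeping collected data says nothing about intervals that generated none, and the planned session mean does not carry out the per-interval definition, however generously that definition is read.

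**Conclusion.** The point holds in limited form. Followed as written, the analysis can score a session stopped early at a high heart rate as in range when the protocol's definition would not. That is a conflict between two sections, not merely a missing detail. Early withdrawers are under-weighted if sessions are pooled.

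Overstatement is the likely direction but is not certain: a patient who stops before heart rate has risen could instead lower the session mean. The size cannot be derived from the documents. The 100% against 40% contrast assumes that all 4 performed intervals were in range and that only recorded intervals form the denominator. The group figures rest on assumed withdrawal, session and in-range rates, and the pooled column assumes pooling. This is a worthwhile and cheap correction to a primary outcome; it does not invalidate the study.

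**What to change.** In the statistical section, replace the session-mean comparison as the main tolerability measure with the following.

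- For each patient who starts HIIT, divide intervals achieved by 10 × sessions started. An interval not performed because the patient stopped early, identified from recorded minutes and stopping reason, counts as not achieved.
- Summarise these proportions across all patients who start, one value per patient, so that sessions are not pooled.
- Report the result beside completion and dropout. As a supplementary summary, show withdrawals by recorded reason: intolerance, unrelated, not given.

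The text should also say what counts as achieved within one interval, and that recorded minutes refer to the 20-minute interval block and not to warm-up or cool-down. Sessions never started stay out of the main score and are covered by the completion, dropout and withdrawal summaries.

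Heart-rate files, minutes and stopping reasons are already collected. Withdrawal reasons may be missing because patients need not give one, hence the separate category. The cost is revised SAP wording, a little more analysis work and a lower reported tolerability figure.
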